## 2.2 Secondary Objectives

To determine if preoperative ZNS is more effective than placebo at preventing temporary changes in cochlear health, synaptopathy, and degraded speech perception in the contralateral ear of patients undergoing drilling during skull base surgery.

To identify a genetic risk profile associated with drilling-induced hearing loss we will survey known genetic markers associated with NIHL including markers in CDH23, PCDH15, EYA4, MYO1A, KCNMA1 and OTOG (Zhang et al., (2019) and zonisamide (ZNS) metabolism, CYP2C9 and CYP2C19 (Saruwatari et al., 2010). If significant associations are observed and validated in a subsequent clinical study, we will optimize drug dosages based on a subject's genetic profile.

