#### 12.5 Pharmacogenetics analysis plan

This analysis will be performed at the end of the trial by Gateway Biotechnology. To identify genetic variants with ZNS protection against hearing loss, we will first use univariate logistic regression analyses to identify potential confounding variables: sex, age, Z-scores of drug concentration, Z-scores of noise intensity and duration, and Z-scores of hearing functions measure immediately following surgery. Single-marker allelic association analyses will be conducted on the two imputed data sets in PLINK v1.07. The data will be analyzed with a logistic regression model on the additive continuous dosage of minor alleles from 0 to 2 to account for uncertainty of imputation. We will combine association results in the two cohorts by performing a genome-wide inverse-variance weighting metaanalysis using PLINK v1.07, and assuming a fixed-effect model. Functional annotation of top-associated markers will be performed with R package NCBI2R 1.4.6 (http://CRAN.Rproject. org/package=NCBI2R), and key regional association plots of meta-analyzed results will be generated. To confirm whether these variants are specific to ZNS response, we will apply CEP SKAT to analyze genetic associations based on Z-scores of audiogram average threshold shifts and DPOAE amplitudes. All genetic variants, including both common and rare variants, will be included in this association study. Age, gender, and noise duration and intensity will be adjusted for the analysis. The analysis will also be performed using hearing data collected two weeks following surgery. The only differences will be a) using the Z scores of ECochG AP amplitude, latency, and width as well as WIN score, and b) using average audiogram threshold shifts and DPOAE amplitudes at 30 days post-treatment. We will also include metabolite profiling data to support potential genotypic responses to drug treatments. To control for confounding effects, these models will be adjusted for age, gender, and noise duration and intensity. Finally, the control and ZNS-treated comparisons will be performed using post-hoc comparisons with a Bonferroni adjustment for multiple comparisons of any ZNS versus none. Statistical analyses will be performed using the CEP-SKAT method in R language, and the statistical software SAS version 9.4 for Windows will be used for additional analysis.

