3.3 Secondary efficacy outcomes

The secondary outcome measures are key audiological and clinical assessments of hearing loss as listed below as continuous level variables.

- DPOAE: Distortion product otoacoustic emissions will be measured at baseline (before surgery), as well as within 8 hours and at 30 days (+/- 3 days) post-surgery to measure both temporary and permanent change in DPOAE amplitude relative to baseline. A change is noted in DPOAE amplitude at any frequency that is significantly greater than the stability of each measurement (i.e., 95% confidence interval of each measurement do not overlap).
- ECochG: Electrocochleography will be measured at baseline (before surgery) and at 30 days (+/- 3 days) post-surgery to measure change in ECochG AP amplitude, latency, and width.
- WIN testing: The Words in Noise Test will be administered at baseline (before surgery) and at 30 days (+/- 3 days) after surgery. The respective scores will be converted to Z-scores to evaluate any change in scores relative to baseline.

The study will also include an exploratory analysis aiming to identify biomarkers of response to ZNS.

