7.1.3 Pharmacogenetics analysis plan

This analysis will be performed at the end of the trial by Gateway Biotechnology. To identify genetic variants associated with ZNS protection against hearing loss, we will utilize genetic and metabolic data collected from patients in a genetic association study. Variables including sex, age, normalized values (Z-scores) of drug plasma concentration, Z-scores of noise intensity and duration, and Z-scores of hearing functions measured immediately following surgery will be included in the analysis of variance. Single-marker allelic association analyses will be conducted on the two imputed data sets using PLINK v1.07. The data will be analyzed with a logistic regression model on the additive continuous dosage of minor alleles from 0 to 2 to account for uncertainty of imputation. We will combine association results in the two cohorts by performing

a genome-wide inverse-variance weighting meta-analysis using PLINK v1.07, and assuming a fixed-effect model. Functional annotation of top-associated markers will be performed with R package NCBI2R 1.4.6 (http://CRAN.Rproject. org/package=NCBI2R), and key regional association plots of meta-analyzed results will be generated. To confirm whether these variants are specific to ZNS response, we will apply CEP SKAT to analyze genetic associations based on Z-scores of audiogram average threshold shifts and DPOAE amplitudes. All genetic variants, including both common and rare variants, will be included in this association study. Age, gender, drug concentration, and noise duration and intensity will be adjusted for the analysis. The analysis will also be performed using hearing data collected two weeks following surgery. The only differences will be a) using the Z scores of ECochG AP amplitude, latency, and width as well as WIN score, and b) using average audiogram threshold shifts and DPOAE amplitudes at 30 days (+/- 3 days) post-treatment. We will also include metabolite profiling data to support potential genotypic responses to drug treatments. To control for confounding effects, these models will be adjusted for age, gender, and noise duration and intensity. Finally, the control and ZNS-treated comparisons will be performed using post-hoc comparisons with a Bonferroni adjustment for multiple comparison testing. Statistical analyses will be performed using the CEP-SKAT method in R language, and the statistical software SAS version 9.4 for Windows will be used for additional analysis.

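### The genetic analysis words its DPOAE and ECochG phenotypes as post-surgery levels, leaves WIN unclear and lists no baseline hearing term, so variants marking pre-existing hearing differences could be read as drilling-related

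*SAP*

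**What the plan says.** The objective in Protocol 2.2 is "To identify a genetic risk profile associated with drilling-induced hearing loss". SAP 2.2.3 repeats it under the heading of exploratory analysis.

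Protocol 12.5 bases the CEP-SKAT step on "genetic associations based on Z-scores of audiogram average threshold shifts and DPOAE amplitudes", and SAP 7.1.3 uses the same words. For the later visit, SAP 7.1.3 specifies "using the Z scores of ECochG AP amplitude, latency, and width as well as WIN score" and "using average audiogram threshold shifts and DPOAE amplitudes at 30 days (+/- 3 days) post-treatment". Only the audiogram measure is named as a shift.

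On adjustment, SAP 7.1.3 says "Age, gender, drug concentration, and noise duration and intensity will be adjusted for the analysis" for CEP-SKAT and "these models will be adjusted for age, gender, and noise duration and intensity" for the follow-up models. Protocol 12.5 has the same lists without drug concentration. Both sections also name hearing function measured immediately after surgery: the SAP as a term in an analysis of variance, the protocol as a possible confounder to screen. No pre-surgery hearing value appears in either section.

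Elsewhere the plan does use baseline. Protocol 5.1 schedules DPOAE, ECochG and WIN before surgery. SAP 3.3 repeats ECochG after surgery "to measure change in ECochG AP amplitude, latency, and width", describes DPOAE as change relative to baseline, and converts WIN to Z-scores in order to assess change. The ANCOVA in SAP 7.1.2 for these outcomes controls for the baseline value.

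**The concern.** Drilling-induced loss is a change. A level measured after surgery carries the subject's pre-existing hearing with it, and turning the level into a Z-score only rescales it, so the association test is the same.

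In the treatment comparison, randomisation balances baseline hearing on average. Genotype has no such protection. The scan targets loci already linked to hearing loss (Protocol 1.4 and 2.2) and extends to all variants, and eligible ears range up to 45 dB HL at 4 kHz (Protocol 3.1), so baseline differences by genotype are plausible. A variant with no role in the response to drilling could then be listed as part of the drilling-loss profile. Between-subject baseline spread can also hide variants that do act through drilling.

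A separate group, Gateway Biotechnology, will run this analysis, so the phenotype definition has to be clear on the page.

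**Working it through.** The documents give no sample size, power or error rate for the genetic analysis, so there is no plan figure to reproduce. What follows is an illustration.

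**Inputs.** N = 234 (SAP 2.3). Assumed, because the documents do not give them: an additive variant with no effect on the shift, explaining a share q of baseline variance, and the baseline-to-post correlation ρ. Tests are two-sided.

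**Formula.** If genotype explains a share R² of the phenotype's variance, λ = √(N·R²/(1−R²)) and the rejection rate at 0.05 is about Φ(λ − 1.96).

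**Model A: stable trait plus independent noise at each visit.**
- Level: R² = q. For q = 5%, λ = √(234×0.05/0.95) = 3.51, rejection 94%. For q = 3%, λ = 2.69, rejection 77% (simulated 76%). Neither depends on ρ.
- Change score: R² = 0, rejection about 5%.
- Baseline covariate: R² = q(1−ρ)²/[(1−q)(1−ρ²)]. For q = 5%, ρ = 0.7 this is 0.0093, λ = 1.48, rejection about 32% (simulated 31%). At ρ = 0.8 it is about 21%.

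**Model B: post value regresses on baseline, Y = ρB + √(1−ρ²)·e.**
- Level: R² = qρ². For q = 5%, rejection is 41%, 68% and 79% at ρ = 0.5, 0.7 and 0.8.
- Change score: variance 2(1−ρ), so R² = q(1−ρ)/2. For q = 5% this is 0.0125, 0.0075 and 0.005, giving about 41%, 26% and 19%.
- Baseline covariate: R² = 0, rejection about 5%.

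**Model C: post value = baseline + independent shift** (2,000 simulated trials, ρ = 0.71 to 0.89).
- Level: 35% to 50% at q = 2%, 68% to 88% at q = 5%, 93% to nearly 100% at q = 10%.
- Change score and baseline covariate: both about 5%.
- Genotype-by-ZNS interaction on the level: 4.7% to 5.9%.

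**Threshold.** At 0.05/8, for the eight genes named in Protocol 2.2, simulation of the Model A level test gives about 47% (q = 3%) and 76% (q = 5%). At an assumed genome-wide 5×10⁻⁸ (critical value 5.45) the same variants give Φ(2.69 − 5.45) = 0.3% and Φ(3.51 − 5.45) = 2.6%. The plan states no threshold for the scan.

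**Power.** For a variant acting only through drilling (0.183 SD, two-sided 0.05, stable-trait structure, 4,000 simulated trials):

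| ρ | Level | Change | Covariate |
|---|---|---|---|
| 0.5 | 0.785 | 0.786 | 0.882 |
| 0.7 | 0.804 | 0.940 | 0.970 |

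The change score breaks even with the level at 2(1−ρ) = 1, that is, ρ = 0.5.

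**The case against.** **The text never says raw values.** This is true. It says Z-scores, without saying what they are standardised against, and SAP 3.3 ties the WIN Z-score to change, so a change reading of WIN is plausible. A reader might infer that all three phenotypes are plainly unreferenced; the documents do not support that for WIN. For DPOAE and ECochG the contrast with threshold shifts in the same sentences makes the level reading the natural one, and SAP 7.1.3 does not refer back to SAP 3.3.

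**Baseline spread is limited.** The note in Protocol 3.2 removes from secondary analyses subjects with DPOAE absent at more than 4 of 10 frequencies, no wave I, or WIN above 14.9 dB SNR, and exclusion 6 bars ear disorders in the tested ear. This narrows the spread but leaves ample variation among retained subjects.

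**A hearing covariate is named.** It is measured after the exposure, when only DPOAE is scheduled, and it is missing from the CEP-SKAT and follow-up adjustment lists. It cannot stand in for baseline.

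**ZNS-response markers.** A reader might infer that baseline-only variants would also be reported as ZNS-response variants. Such a variant shifts all arms equally, and a genotype-by-ZNS test keeps about 5% even on levels. The risk arises only if response is claimed without that test. The plan states no interaction term, and it leaves unclear how its post-hoc control-versus-ZNS comparison relates to genotype.

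**Consequences.** A reader might infer a direct route to dosing. Both documents require validation in a later clinical study first.

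**Which correction is better.** It is tempting to prescribe the change score outright. Models A and B show that each correction can leave bias under the other's structure, so the ranking is not settled. A gain from 80% to 90% power at ρ = 0.5 belongs to the baseline covariate; the change score gains nothing there.

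**Conclusion.** The point holds as a should-fix item. As worded, the DPOAE and ECochG genetic phenotypes are post-surgery levels, WIN is ambiguous, and no baseline hearing value is listed, although the values are collected and the SAP uses them elsewhere. Variants that mark pre-existing hearing could therefore be read as drilling-related.

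The size rests on assumptions. For a variant explaining 5% of baseline variance, nominal 0.05 rejection of the level runs from 41% to 94% across the three models; a smaller variant effect lowers it, and at the assumed genome-wide threshold it is 2.6% or less. The audiogram phenotype is already a shift and is not affected. The outcome of the single-marker logistic model is not stated, so nothing can be concluded about it here. The analysis is exploratory in the SAP (a secondary objective in the protocol), and the primary result and the treatment comparisons do not depend on it.

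**What to change.** In SAP 7.1.3 and Protocol 12.5:

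1. Make the DPOAE, ECochG and WIN phenotypes baseline-referenced, either as change from baseline (as in SAP 3.3) or by adding the subject's own baseline value as a covariate (as in SAP 7.1.2). Name one as the main analysis and report the other as a sensitivity analysis. A variant flagged by only one should be described as such.
2. State what each Z-score is standardised against and at which visit.
3. Base any claim of ZNS response on a stated genotype-by-ZNS comparison.

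The cost is wording in two documents; no new data are needed. Subjects without a baseline value drop out of that phenotype. If ρ is below 0.5, a change score is noisier than the level (65% against 79% power at ρ = 0.3 in the same setting), which is a reason to look at the observed correlation, without reference to genotype, before choosing the main analysis.

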#### 3.3 Inclusion of Women and Minorities

Both men and women and members of all races and ethnic groups are eligible for this trial.

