6.2 Demographics Characteristics

Demographic characteristics will be summarized descriptively by treatment group for the Safety Sample Set, including:

- Age (years) at time of consent
- Sex
- Ethnicity
- Race

Demographics characteristics will be listed.

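### The genetic models name no ancestry control although all races and ethnic groups are eligible, so risk-marker associations can be falsely positive

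*SAP*

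**What the plan says.** The genetic plan appears in SAP 7.1.3 and, nearly identically, in Protocol 12.5. It has three parts: single-marker logistic regression on allele dosage, a fixed-effect inverse-variance meta-analysis, and CEP-SKAT on Z-scores of threshold shift and DPOAE amplitude.

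Covariates are named in three places.

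- **Opening step.** The SAP enters "Variables including sex, age, normalized values (Z-scores) of drug plasma concentration" together with Z-scores of noise and of hearing function immediately after surgery. The protocol screens a similar list by univariate logistic regression for potential confounders.
- **CEP-SKAT.** The SAP says "Age, gender, drug concentration, and noise duration and intensity will be adjusted for the analysis". The protocol omits drug concentration: "Age, gender, and noise duration and intensity will be adjusted for the analysis".
- **The confounding rule, in both documents.** "To control for confounding effects, these models will be adjusted for age, gender, and noise duration and intensity".

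On scope, the SAP says "All genetic variants, including both common and rare variants, will be included in this association study".

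On population, Protocol 3.3 says "Both men and women and members of all races and ethnic groups are eligible for this trial". SAP 6.2 lists race and ethnicity among the demographic variables, for descriptive summary by arm only.

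**The concern.** Treatment is randomised in this trial; genotype is not. Allele frequencies can differ between ancestry groups. If PTS risk differs too, for example through past noise exposure, baseline hearing or susceptibility, a variant that merely marks ancestry will be correlated with PTS.

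The listed covariates do not block that path. Noise duration and intensity match what Protocol 5.4 records during surgery. Noise-exposure history and pre-operative hearing are covariates in the clinical models of SAP 7.1.1 and 7.1.2 but are not on the genetic list. Race, ethnicity, genetic principal components, genomic control, and restriction or stratification by ancestry appear nowhere in the genetic plan.

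The background section makes the gap easier to see. Protocol 1.4 says the approaches of the earlier hearing-loss genetics work will be carried over. There, the treated group and both control cohorts were white women, so ancestry mixing was limited by restriction. This trial lifts the restriction and puts no adjustment in its place.

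At stake is the genetic risk profile, a secondary objective in Protocol 2.2 and an exploratory analysis in SAP 2.2.3. False markers carried forward would waste effort in the later validation study.

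**Working it through.** **No figure to reproduce.** Neither document states a power, sample size or marker-level significance threshold for the genetic analysis. The check is therefore whether the omission can bias a marker test, and by how much under stated assumptions.

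**Inputs from the documents.** N = 234 (all arms) or 156 (two arms, 78 + 78). Design PTS rates are 50% on placebo and 25% on each ZNS arm, which average (50 + 25 + 25)/3 = 33%.

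**Assumed inputs.** Two ancestry groups, with share w = 20% or 30% in the smaller; allele frequencies f1 and f2; PTS risks r1 and r2. There is no association between allele and PTS within either group.

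**Formula.** For allele count G and PTS indicator Y, the covariance created by mixing is

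cov = w(1 − w) × 2(f2 − f1) × (r2 − r1).

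It is zero if either difference is zero. The unadjusted trend statistic is then centred near d = √N × cov / √(Var G × Var Y) instead of 0. The nominal two-sided 5% test is positive with probability about Φ(d − 1.96) + Φ(−d − 1.96). Here Var G = (1 − w)·2f1(1 − f1) + w·2f2(1 − f2) + w(1 − w)·4(f2 − f1)², and Var Y = r(1 − r) with r the pooled risk.

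**Worked middle case.** N = 234, w = 0.3, f = 0.1 v 0.3, r = 0.40 v 0.60.

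- cov = 0.21 × 0.4 × 0.2 = 0.0168
- Var G = 0.126 + 0.126 + 0.0336 = 0.2856
- Pooled r = 0.46, so Var Y = 0.46 × 0.54 = 0.2484
- d = 15.30 × 0.0168 / √(0.2856 × 0.2484) = 0.965
- False-positive rate ≈ Φ(−0.995) + Φ(−2.925) ≈ 0.16

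Simulation of the same setting gives 0.161.

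**Simulated false-positive rates at nominal 0.05** (10,000 runs per setting, additive score test):

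| Setting | Unadjusted | Ancestry-stratified |
|---|---|---|
| N 234, w 0.2, f 0.1 v 0.2, PTS 45% v 55% | 0.055 | 0.051 |
| N 156, w 0.2, f 0.1 v 0.3, PTS 40% v 60% | 0.095 | 0.053 |
| N 234, w 0.3, f 0.1 v 0.3, PTS 40% v 60% | 0.161 | 0.049 |
| N 234, w 0.3, f 0.1 v 0.5, PTS 35% v 65% | 0.693 | 0.047 |

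Across all settings in which both quantities differ, the unadjusted rate runs from 0.051 to 0.693. Where only one differs, or neither, it is 0.044 to 0.055. The stratified rate is 0.045 to 0.057 throughout.

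**Settings nearer the pooled 33% rate (N = 234).** With 36% v 26% PTS, allele frequencies 0.2 v 0.3 give 5% to 6%, and 0.2 v 0.4 give 6% to 7%. A separate set of logistic fits (3,000 per scenario, PTS 36% v 21–26% or 38% v 18%, frequencies 0.2 v 0.4 or 0.1 v 0.5) gives 0.057 to 0.391 unadjusted and 0.046 to 0.054 with an ancestry term.

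**Genotype-by-treatment test.** With frequencies 0.1 v 0.5, a large ancestry difference in PTS odds and a common ZNS odds ratio, the null interaction test is positive in 5.1% of trials without ancestry adjustment. The genotype main-effect test is positive in 27%.

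**The case against.** The strongest reply is that the bias is conditional and the analysis modest. Much of this stands.

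- **PTS risk may not vary by ancestry.** The documents offer no evidence that it does. PTS is a change from the subject's own baseline, eligibility restricts baseline hearing, and surgical noise is adjusted. These features narrow the path without closing it.
- **The covariate list is longer than age, gender and noise.** The SAP adds drug concentration in CEP-SKAT, and the opening step lists post-surgery hearing. The covariates of the single-marker logistic model are not spelled out, and which models the confounding sentence governs is not fully clear. None of the named variables stands in for ancestry.
- **Scope is uncertain.** The objective names markers in six hearing-loss genes and two metabolism genes, while the analysis text describes a genome-wide meta-analysis. The plan says "We will combine association results in the two cohorts by performing" that meta-analysis, but neither document defines those cohorts. Nothing says they are ancestry groups.
- **The simulations simplify the plan.** They use binary PTS without the age, gender and noise covariates, whereas CEP-SKAT uses continuous Z-scores. The largest rates need extreme pairings of inputs.

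A reader might infer more: that the risk profile will contain ancestry markers, that p-values will miss a stated error rate, or that findings on response to ZNS are compromised. The documents do not support these. The first needs both differences to be present, and neither is documented. For the second, no marker-level threshold is stated; the Bonferroni wording concerns the control versus ZNS comparisons. For the third, treatment is randomised, and a genotype-by-treatment test kept its 5% level in the case tried, which assumed a common ZNS effect.

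**Conclusion.** The point holds in a limited form. Both documents give an explicit list of covariates to control confounding, eligibility is unrestricted by ancestry, and the genetic models contain no ancestry control. Genotype main-effect associations can therefore be falsely positive if allele frequency and PTS risk (or threshold shift) both differ between ancestry groups.

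The size cannot be read from the documents. Under the assumed inputs it runs from almost no inflation to several-fold inflation of a nominal 5% test, and adjustment removes it.

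The weight is low. The randomised primary comparison is untouched, the SAP classes the analysis as exploratory, and both documents require validation in a later study before any use for dosing. It is worth correcting because the correction is cheap.

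**What to change.** In SAP 7.1.3 and Protocol 12.5, add genotype-derived ancestry principal components to each single-marker logistic model and each CEP-SKAT model, with the number of components fixed in advance. If only candidate markers are typed, components may not be estimable; use recorded race and ethnicity instead.

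Fit these terms within each cohort, before the fixed-effect step. Inverse-variance pooling combines summary estimates, so covariates cannot be added there. This requires the SAP to say what the two cohorts are.

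The cost is a wording change and a few degrees of freedom per model. No extra visits, samples or subjects are needed: components come from the same genotype data, and race and ethnicity are already listed in SAP 6.2.
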